412 • Clinical evaluation of patch test reactions.

413 • Clinical photography.

414 **4. STATISTICS**

415 **4.1. Methods**

416 The analysis plan and statistical analysis will be carried out by the trial's investigators. Any

417 deviations from the original plan will be documented and justified in the final report.

418 The results will be analyzed based on treatment code using a statistical analysis plan finalised

419 prior to revealing the coded allocation sequence. Only after the analysis is complete will the

420 actual treatment arms corresponding to the treatment codes be revealed. The analysis will be

421 conducted by per protocol.

422

423 **4.2. Sample size**

424 A total of 20 participants will be recruited to the study (10 per arm). This should be sufficient to

425 detect a reduction in clinical score of at least one scoring point at 80% power and 95%

426 significance level.

427

428 **5. ADVERSE EVENTS**

429 **5.1. Definitions**

430 An **adverse event (AE)** is any unfavourable and unintended sign, symptom, syndrome or illness

431 that develops or worsens during the period of observation in the study.

432 An AE does include a / an:

- 433 1. Exacerbation of a pre-existing illness.
- 434 2. Increase in frequency or intensity of a pre-existing episodic event or condition.
- 435 3. Condition detected or diagnosed after study drug administration even though it may
- 436 have been present prior to the start of the study.
- 437 4. Continuous persistent disease or symptoms present at baseline that worsen following
- 438 the start of the study.

439 An AE does not include a / an:

- 440 1. medical or surgical procedure (e.g., surgery, endoscopy, tooth extraction, transfusion);
441 but the condition that lead to the procedure is an AE.
- 442 2. pre-existing disease or conditions present or detected at the start of the study that did
443 not worsen.
- 444 3. situations where an untoward medical occurrence has not occurred (e.g.,
445 hospitalisations for cosmetic elective surgery, social and / or convenience admissions).
- 446 4. disease or disorder being studied or sign or symptom associated with the disease or
447 disorder unless more severe than expected for the participant's condition.
- 448 5. overdose of concurrent medication without any signs or symptoms.

449 **A Serious Adverse Event (SAE)** is any adverse event occurring that results in any of the
450 following outcomes:

- 451 • Death
- 452 • life-threatening

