- 453 • Inpatient hospitalisation or prolongation of existing hospitalisation
- 454 • Persistent or significant disability / incapacity
- 455 • A congenital anomaly or birth defect in the offspring of a participant
- 456 • Other medical events may be considered to be a SAE if they require medical or surgical
457 intervention to prevent one of the outcomes listed in this definition.

458 All adverse events will be assessed for seriousness, expectedness and causality (not related,
459 possibly related, probably related or definitely related). An adverse event whose causal
460 relationship to the study drug is assessed by the Chief Investigator as "possible", "probable", or

461 “definite” is an Adverse Reaction (AR). If the AR is classed as serious then it is a Serious
462 Adverse Reaction (SAR). A distinction is drawn between serious and severe AEs. Severity is a
463 measure of intensity whereas seriousness is defined using the criteria above. Hence, a severe
464 AE need not necessarily be serious. All adverse events will be recorded and closely monitored
465 until resolution, stabilisation, or until it has been shown that the study medication or treatment is
466 not the cause. The summary product characteristics for Kineret® will be used as a reference
467 document to assess if an AE or SAE is expected or unexpected.

468 **5.2. Causality**

469 **Not related or unlikely:** a clinical event including laboratory test abnormality with temporal
470 relationship to trial treatment administration which makes a causal relationship incompatible or
471 for which other drugs, chemicals or disease provide a plausible explanation. This will be
472 counted as “unrelated” for notification purposes.

473 **Possible:** a clinical event, including laboratory test abnormality, with temporal relationship to
474 trial treatment administration which makes a causal relationship a reasonable possibility, but
475 which could also be explained by other drugs, chemicals or concurrent disease. This will be
476 counted as “related” for notification purposes.

477 **Probable:** a clinical event, including laboratory test abnormality, with temporal relationship to
478 trial treatment administration which makes a causal relationship a reasonable possibility, and is
479 unlikely to be due to other drugs, chemicals or concurrent disease. This will be counted as
480 “related” for notification purposes.

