481 **Definite:** a clinical event, including laboratory test abnormality, with temporal relationship to trial
482 treatment administration which makes a causal relationship a reasonable possibility, and which
483 can definitely not be attributed to other causes. This will be counted as “related” for notification
484 purposes.

485 An AE whose causal relationship to the study investigational medical product (IMP) is assessed
486 by the Chief Investigator as “possible”, “probable”, or “definite” is an Adverse Drug Reaction.

487 With regard to the criteria above, medical and scientific judgment shall be used in deciding
488 whether prompt reporting is appropriate in that situation.

489 **5.3. Reporting of Adverse Events**

490 Participants will be asked to contact the study site immediately in the event of any significant
491 adverse event. The Chief Investigator shall be informed immediately of any reportable serious
492 adverse reactions and shall determine seriousness and causality in conjunction with any
493 treating medical practitioners.

494 In the event of a pregnancy occurring in a trial participant or the partner of a trial participant
495 monitoring shall occur during the pregnancy and after delivery to ascertain any trial related
496 adverse events in the mother or the offspring. Where it is the partner of a trial participant
497 consent will be obtained for this observation from both the partner and her medical practitioner.

498 All serious adverse reactions will be recorded and reported to the Danish Medicines Agency
499 (DMA) and regional ethics committees (REC) as part of the regular mandatory reports. SUSARs
500 will be reported by e-form within the statutory timeframes to the DMA and REC as stated below.
501 The Chief Investigator shall be responsible for all adverse event reporting.

502 **5.4. Suspected Unexpected Serious Adverse Reaction (SUSARs)**

503 A serious adverse reaction (SAR) that is unexpected (i.e. not a known side effect of the study
504 drug) is classed as Suspected Unexpected Serious Adverse Reaction. All SUSARs will be
505 reported immediately to the Chief Investigator and will require expedited reporting to the
506 authorities as described below.

507 The Chief Investigator will:

- 508 • Assess the event for seriousness, expectedness and relatedness to the study IMP.
- 509 • Take appropriate medical action, which may include halting the trial.

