- 510 • If the event is deemed a SUSAR, shall, within seven days, complete the CIOMS form
511 and send to the DMA.
- 512 • Shall inform the REC using the relevant reporting form found on the REC's web page
513 within seven days of knowledge of the event.
- 514 • Shall, within a further eight days send any follow-up information and reports to the DMA
515 and REC.
- 516 • Make any amendments as required to the study protocol and inform the ethics and
517 regulatory authorities as required.

518 **5.5. Collection of Adverse Event Data**

519 This study investigates a widely used drug, anakinra, for which the side-effect profile is well
520 established. For this reason, only adverse events that are known side-effects will be collected
521 (detailed in section 4.2.4, Known side effects) i.e. only adverse reactions will be collected.

522 At each mandatory study visit, the investigator will record whether the participant had
523 experienced any of the reportable adverse events. The investigator can also record any other
524 significant adverse events that are not listed if deemed clinically relevant.

525 All available sources of information will be used to collect information on adverse events
526 including hospital notes, the participant diary and discussion with the participant. Any adverse
527 events reported will be graded according to a modified version of the Common Terminology
528 Criteria for Adverse Events v3.0.

529 **6. Ethics Committee and Regulatory Aspects**

530 **6.1. Ethical and Regulatory Approval**

531 The trial will not be initiated before the protocol, informed consent forms and participant and
532 information sheets have received approval / favourable opinion from the DMA and REC.

533 The trial will be conducted in accordance with the ethical principles that have their origin in the
534 Declaration of Helsinki, 1996; the principles of Good Clinical Practice, in accordance with the
535 Medicines for Human Use Regulations, Statutory Instrument 2004, 1031 and its subsequent
536 amendments.

537 **6.3. Case Report Forms**

538 Each participant will be assigned a trial identity code number, allocated at randomisation, for
539 use on the case report forms (CRFs), other trial documents and the study database. The
540 documents and database will also use their initials (of first and last names separated by a
541 hyphen or a middle name initial when available) and date of birth (dd/mm/yy).

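### Section 5.5 limits adverse event collection to known side effects, against section 5.1, and the schedule marks recording at only 5 of 12 visits

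*Combined protocol and SAP*

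**What the plan says.** **Scope.** Section 5.1 defines an adverse event as an unfavourable, unintended occurrence "that develops or worsens during the period of observation in the study". It states "All adverse events will be recorded and closely monitored" and "All adverse events will be assessed for seriousness, expectedness and causality"; the causality categories include not related. An adverse reaction is an adverse event judged possibly, probably or definitely related.

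Section 5.5, citing the drug's established safety profile, states "For this reason, only adverse events that are known side-effects will be collected", and continues "i.e. only adverse reactions will be collected". For the list it points to section 4.2.4. No such section exists (4.2 is the sample size); the list is in section 1.2.4. Section 5.5 lets the investigator add other significant events judged clinically relevant, and names hospital notes, the diary and discussion with the participant as sources.

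Section 5.3 asks participants to contact the site about significant events and requires that "All serious adverse reactions will be recorded and reported to the Danish Medicines Agency". Section 5.4 defines a SUSAR as "A serious adverse reaction (SAR) that is unexpected (i.e. not a known side effect of the study" drug).

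**Timing.** Section 5.5 states "At each mandatory study visit, the investigator will record whether the participant had" experienced a reportable event. The section 3.9.1 table marks recording on days 21 to 25 only, and the visit lists in section 3.9 agree. The list for day 44 has the diary collected and medical problems recorded from it.

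**The concern.** Site staff have two incompatible instructions on what to collect and two on when to collect it. If they follow section 5.5, the trial has no routine question that would bring out an event missing from a short list, although the drug is being tested in a new indication. Expectedness and causality can be assessed only for events that have been captured, so the assessment in 5.1 and the SUSAR pathway in 5.4 depend on what 5.5 lets through.

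What is at stake is the completeness of the safety record and the reliability of SUSAR detection. The protocol plans no between-arm safety test, so no inferential result depends on this.

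**Working it through.** **1. Scope, passages side by side**

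| Section | What is captured | Order |
|---|---|---|
| 5.1 | All adverse events, including those judged not related | Record, then judge |
| 5.5, known-side-effects limit | Known side effects in 1.2.4 | List decides before recording |
| 5.5, adverse-reactions limit | Adverse reactions | Relatedness judged before recording |
| 5.3 | All serious adverse reactions, listed or not | Record and report |
| 5.4 | SUSARs, by definition not known side effects | Assess and report |

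The two limits in 5.5 are not equivalent. A known side effect is defined by a list; an adverse reaction is defined in 5.1 by causality. Under the known-side-effects limit a SUSAR lies outside routine collection. Under the adverse-reactions limit it lies inside, but only once someone has judged the event related, which reverses the order in 5.1.

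**2. How narrow the list is**

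Section 1.2.4 has five entries: headache, injection-site reaction, serious infections, neutropenia and allergic reactions. Infection shows the gap within the protocol's own text. The list names serious infections only, section 3.8.7 ends study drug for any infection, and section 7.4 calls infection the most common treatment risk. Under the known-side-effects limit in 5.5, a non-serious infection is not a listed event. The stopping rule itself is not questioned here.

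**3. Visit count**

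Inputs are the columns and marks of the 3.9.1 table, checked against the visit lists in 3.9.

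- Visits: days 0, 2, 3, 20, 21, 22, 23, 24, 25, 42, 44, 45 = 12. This reproduces the 12 visits stated in sections 3.1 and 3.6.1.
- Marked for recording: days 21, 22, 23, 24, 25 = 5, so 5/12 = 41.7%.
- Unmarked: days 0, 2, 3, 20, 42, 44, 45 = 7.
- From the first-dose visit (day 20) onward: 9 visits, 5 marked. The unmarked ones are days 20, 42, 44 and 45.
- After the first-dose visit: 8 visits, of which 5 are marked, 1 (day 44) has the diary review, and 2 (days 42 and 45) list nothing.
- Dosing days 20 to 25: 6 visits, 5 marked; day 20 is not.
- After the last dose: 3 visits, none marked, although biopsies are taken on days 42 and 44.

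**4. Gaps in time**

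- Last dose to the next listed item of any kind: 44 − 25 = 19 days.
- Last marked visit to last visit: 45 − 25 = 20 days.
- Section 3.1 has stitches removed 8 to 10 days after biopsy. The earliest is 42 + 8 = day 50 and the latest 44 + 10 = day 54, which is 5 to 9 days after the day 45 visit. No recording item is listed after the diary is handed in on day 44.

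**5. Terms**

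The visit lists ask for adverse events on days 21, 24 and 25 and adverse reactions on days 22 and 23. The table uses adverse reactions for all five.

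**The case against.** Several points on the other side have weight.

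- **Denominator.** Days 0, 2 and 3 precede the first dose, so no drug reaction can occur then, and the term mandatory is undefined. This stands in part: for events after treatment starts, 5 of 9, or 5 of 8 without day 20, is fairer than 5 of 12. Reading mandatory as dosing visits does not rescue the schedule, because day 20 is a dosing visit and is unmarked.
- **Diary.** Every participant is given a diary on day 0 for medical problems of any kind, and these are recorded on day 44. This also stands in part: the 19 days are a gap between clinic items, not in diary coverage. But the diary is reviewed once, near the end, and covers nothing after it is handed in.
- **SUSAR safeguards.** Section 5.3 requires serious reactions to be recorded, 5.4 sets a reporting route, and 5.5 includes discussion with the participant. These are real safeguards. They do not amount to a routine question about unlisted events, and what discussion is meant to bring out is limited by the same section. The adverse-reactions limit in 5.5 would admit a SUSAR, or a mild infection judged possibly related, but only after that judgement.
- **Recording versus data collection.** The protocol may intend clinical notes for all events and trial data for a subset; section 3.9.3 treats screening laboratory results that way. Section 5 does not say so.
- **Selective collection as a choice.** For a well-characterised drug the sponsor might defend it. Sections 5.1, 5.3 and 5.4 would then have to say so, and they currently say the opposite.
- **Other follow-up.** Section 3.7.6 follows those who withdraw from treatment for two weeks, and 5.1 follows events to resolution. The first covers only withdrawals; the second helps only once an event has been recorded.

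**Conclusion.** The concern holds. Sections 5.1 and 5.5 contradict each other on which events are collected, and 5.5 contradicts itself by giving two different limits. Section 5.5 and the schedule also disagree on timing: recording is marked at 5 of 12 visits, or 5 of 9 from the first-dose visit, with the first dosing day and all three post-treatment visits left out.

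The visit count is exact, and the visit lists confirm the table. Its interpretation depends on what mandatory means, which the protocol does not state. The practical loss depends on how much the diary, self-report and the investigator's discretion recover, which the documents do not allow one to quantify. This should be fixed: it concerns the completeness of the safety data and does not bear on the efficacy analysis. The stitch-removal timing, the mixed terms and the wrong cross-reference are minor, and the conclusion does not rest on them.

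**What to change.** 1. In section 5.5, delete the restriction to known side effects and its restatement as adverse reactions. State that all adverse events are recorded over the period of observation in 5.1, and only then assessed for seriousness, causality and expectedness against the product summary. This brings 5.5 into line with 5.1, 5.3 and 5.4.
2. State the first and last day of the period of observation, including whether it runs to stitch removal.
3. Define mandatory visit, and add the recording item to the 3.9.1 table and the visit lists at least on days 20, 42, 44 and 45.
4. Use the single term adverse events throughout section 3.9, and correct the cross-reference to section 1.2.4.

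The cost is protocol and case report form wording, plus four more recording points per participant at visits that already take place (4 × 20 = 80 in all). The downside is some additional entries for non-serious events. No change to dosing, stopping or other clinical management is involved.
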